### **5.3.2. Efficacy Variables**

The study was not designed to make an efficacy assessment. However, any tumor response data will be tabulated according to study part and patient cohort.

Exploratory efficacy analysis will be performed to investigate antitumor activity within each combination arm. Response and disease progression will be evaluated using Response Evaluation Criteria in Solid Tumors (RECIST) version 1.1 (Eisenhauer et al. 2009) for all tumors with the exception of CNS tumors. RANO (Wen et al. 2010) or Macdonald (Macdonald et al. 1990) criteria should be used for CNS tumors.

**Overall Response Rate (ORR)** is defined as the percentage of patients achieving a best overall response of either Complete Response (CR) or Partial Response (PR), as determined by RECIST 1.1/RANO/Macdonald criteria. The best overall response is the best response from the start of the treatment until PD/recurrence.

**Disease control rate (DCR)** is defined as the percentage of patients achieving a best overall response of CR, PR, or SD. Patients who do not have any postbaseline tumor response assessments for any reason are considered non-responders and are included in the denominator when calculating the response rate.

**Duration of Overall Response** is measured from the time measurement criteria are first met for CR or PR (whichever is first recorded) until the first date the criteria is met for PD is objectively documented, or initiation of other/additional antitumor therapy is first reported, or death. Patients who do not relapse are censored at the day of their last tumor assessment.

**Progression-free survival (PFS)** is defined as the time from the date of first study dose to the first date of radiologic disease progression or death due to any cause. [Table JGDN.5.1](#) defines the rules of censoring to be applied to PFS.

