6.2.1. Primary Endpoint

Primary endpoint is defined as DLT and PK data exposure matching. The primary endpoint analysis will occur after the final patient enrolled has been evaluated for at least 2 cycles.

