8.3. Efficacy Evaluations

A secondary objective of the study is to document any antitumor activity. Imaging studies and tumor assessments are to be obtained every 2 cycles (± 7 days), until documented progression for patients with complete response (CR), partial response (PR), or stable disease (SD).

For patients who have discontinued study treatment due to toxicity or reasons other than progressive disease, imaging studies and tumor assessments are to be obtained every 6 weeks (± 7 days) until progression. For these patients, details on subsequent anticancer treatment (start/stop dates and treatments administered) and first post-study treatment disease progression date should be recorded.

Each patient will be assessed by one or more of the following radiologic tests for tumor measurement:

- Computed tomography (CT) scan
- Magnetic resonance imaging (MRI)
- Chest x-ray

Each patient's full extent of disease will also be assessed with the following:

- Tumor measurement by RECIST v1.1 (Eisenhauer et al. 2009) should be used for all tumors with the exception of CNS tumors. RANO (Wen et al. 2010) or Macdonald (Macdonald et al. 1990) criteria should be used for CNS tumors.
- Evaluation of tumor markers, if indicated
- Evaluation of performance status (Lansky [Lansky et al. 1987] or Karnofsky [Karnofsky et al. 1948] scale)

To confirm objective responses, all lesions should be radiologically assessed, and the same radiologic method used for the initial response determination should be repeated at least 6 weeks (2 cycles) following the initial observation of an objective response, using the sample method that was used at baseline. If a patient is discontinued from the study, repeat radiology assessments may be omitted if clear clinical signs of progressive disease are present.

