Progressive Disease (PD): At least a 20% increase in the sum of the diameters of target lesions, taking as reference the smallest sum on study (including the baseline sum if that is the smallest). In addition to the relative increase of 20%, the sum must also demonstrate an absolute increase of at least 5 mm. The appearance of one or more new lesions is also considered progression.

For equivocal findings of progression (for example, very small and uncertain new lesions; cystic changes or necrosis in existing lesions), treatment may continue until the next scheduled assessment. If at the next scheduled assessment, progression is confirmed, the date of progression should be the earlier date when progression was suspected.

Stable Disease (SD): Neither sufficient shrinkage to qualify for PR nor sufficient increase to qualify for PD, taking as reference the smallest sum diameters while on study.

Not Evaluable: When an incomplete radiologic assessment of target lesions is performed or there is a change in the method of measurement from baseline that impacts the ability to make a reliable evaluation of response.

Evaluation of Nontarget Lesions

Complete Response: Disappearance of all nontarget lesions and normalization of tumor marker level. All lymph nodes must be non-pathological or normal in size (<10mm short axis).

Non-CR/ non-PD: Persistence of 1 or more nontarget lesions and/or maintenance of tumor marker level above the normal limits.

Progressive Disease: Unequivocal progression of existing nontarget lesions. The appearance of 1 or more new lesions is also considered progression.

Not Evaluable: When a change in method of measurement from baseline occurs and impacts the ability to make a reliable evaluation of response.

Evaluation of Best Overall Response

The best overall response is the best response recorded from the start of the study treatment until the earliest of objective progression or start of new anticancer therapy, taking into account any requirement for confirmation. The patient's best overall response assignment will depend on the findings of both target and nontarget disease and will also take into consideration the appearance of new lesions. The Best Overall Response will be calculated via an algorithm using the assessment responses provided by the investigator over the course of the trial.

Time Point Response

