The main goal of confirmation of objective response in clinical trials is to avoid overestimating the response rate observed. The confirmation of response is particularly important in *nonrandomized trials* where response (CR/PR) is the primary end point. In this setting, to be assigned a status of PR/CR, changes in tumor measurements must be confirmed by repeat assessments that should be performed no less than 4 weeks after the criteria for response are first met. To confirm a response of CR, a full assessment of all target and nontarget lesions that were present at baseline must occur, including those measured by bone scan. To confirm a PR or SD, a full assessment of target lesions that were present at baseline must occur; assessment of nontargets is not required.

However, in *randomized trial* (Phase 2 or 3) or studies where SD or progression is the primary endpoints, confirmation of response is not required. But, elimination of the requirement may increase the importance of central review to protect against bias, in particular of studies which are not blinded.

In the case of SD, follow-up measurements must have met the SD criteria at least once after start of treatment at a minimum interval not less than 6 weeks measured from first dose.

Duration of Overall Response

The duration of overall response is measured from the time measurement criteria are first met for CR or PR (whichever is first recorded) until the first date that disease is recurrent or objective progression is observed (taking as reference for PD the smallest measurements recorded on study).

The duration of overall CR is measured from the time measurement criteria are first met for CR until the first date that recurrent disease is objectively documented.

Duration of Stable Disease

Stable disease is measured from the start of the treatment (in randomized trials, from date of randomization) until the criteria for objective progression are met, taking as reference the smallest sum on study (if the baseline sum is the smallest, that is the reference for calculation of PD).

Independent Review of Response and Progression

When objective response (CR + PR) is the primary end point, and when key drug development decisions are based on the observation of a minimum number of responders, it is recommended that all claimed responses be reviewed by an expert(s) independent of the study. If the study is a randomized trial, ideally reviewers should be blinded to treatment assignment.

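### The SAP's best overall response has no stop at new anticancer therapy and no confirmation rule, which conflicts with the protocol and with the SAP's own duration-of-response and PFS rules

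*SAP*

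**What the plan says.** SAP 5.3.2 defines ORR as the share of patients whose best overall response is CR or PR, "as determined by RECIST 1.1/RANO/Macdonald criteria", and adds: "The best overall response is the best response from the start of the treatment until PD/recurrence". Neither 5.3.2 nor 5.8 mentions confirmation. SAP 5.8 tabulates ORR and DCR with 90% exact intervals by cohort and combination arm.

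The protocol differs in three places.

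- Attachment 8 runs best overall response "until the earliest of objective progression or start of new anticancer therapy, taking into account any requirement for confirmation".
- Section 8.3 says that, to confirm a response, the same radiologic method "should be repeated at least 6 weeks (2 cycles) following the initial observation of an objective response".
- Attachment 8 also describes "repeat assessments that should be performed no less than 4 weeks after the criteria for response are first met", in text about nonrandomized trials "where response (CR/PR) is the primary end point". For this trial, section 6.2.1 states: "Primary endpoint is defined as DLT and PK data exposure matching".

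Attachment 8 further requires that stable disease be met at least once no earlier than 6 weeks from first dose. The SAP has no such minimum.

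**The concern.** Protocol 10.7 leaves the details of the efficacy analysis to the SAP, so the SAP sentence is the one that will be programmed. Read literally, it credits any CR, PR or SD recorded before progression, even on a scan taken after the patient has started another anticancer treatment, and it counts a response seen on a single scan.

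ORR is named in the protocol's secondary objectives. The study has no control arm, and best overall response is derived from investigator assessments, so nothing offsets an over-count. If the rule is settled only after responses are known, the choice can also be influenced by the data.

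**Working it through.** The documents give no target ORR, power or efficacy threshold, so there is no planned figure to reproduce. The check compares the texts and then sizes the effect.

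**1. Treatment of new anticancer therapy**

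- Protocol Attachment 8, best overall response: stops at new therapy.
- SAP 5.3.2, duration of response: new therapy ends it.
- SAP Table JGDN.5.1, PFS: new therapy without progression or death within 14 days leads to censoring at an assessment before new therapy plus 14 days.
- SAP 5.3.2, best overall response: no stop.

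Under the SAP alone, a patient could become a responder on a scan dated after that patient's PFS was censored.

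**2. Whether such scans can exist**

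Other anticancer treatment is barred during study treatment (protocol 7.5), so the question concerns patients who stop for reasons other than progression. For them:

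- Protocol 8.3: imaging every 6 weeks until progression.
- Attachment 1, follow-up schedule, footnote b: until progression.
- Attachment 1, follow-up schedule, imaging comment: until progression or other anticancer therapy.

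Two texts allow scans on a later therapy and one does not.

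**3. Spacing of on-schedule scans**

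Inputs: a scan every 2 cycles of 21 days (42 days), window ±7 days (protocol 8.3). The Part C doxorubicin schedule in Attachment 1 has −7 days only. Assumptions: no cycle delays, windows anchored to the schedule, whole in-window days equally likely.

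Gap between adjacent scans = 42 + b − a, where a and b are the two offsets.

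- ±7 days: range 42 − 14 = 28 to 42 + 14 = 56 days. There are 15 × 15 = 225 pairs. The gap is below 42 when b < a, which is 15 × 14 / 2 = 105 pairs, and 105/225 = 46.7%. None is below 28.
- −7 to 0 days: range 35 to 49 days. Of 8 × 8 = 64 pairs, 8 × 7 / 2 = 28 fall below 42, and 28/64 = 43.8%.

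The scan after that is 84 ± 14 days from the first, so at least 70 days later. A response that persists can still be confirmed there under the 6-week rule.

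**4. Effect on ORR**

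One patient is 1/20 = 5.0 points at the goal of about 20 per combination arm (protocol 6.2), or 1/15 = 6.7 points at the 15 per arm of Parts B and C. The exact 90% limits are the 0.05 quantile of Beta(x, n − x + 1) and the 0.95 quantile of Beta(x + 1, n − x). The counts below are assumed for illustration:

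- 4/20 counted without confirmation: 20.0% (7.1 to 40.1)
- 3/20 confirmed: 15.0% (4.2 to 34.4)
- 2/20 confirmed: 10.0% (1.8 to 28.3)

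**5. Effect on DCR**

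An unconfirmed CR/PR normally falls back to SD and stays in DCR. DCR changes only if the 6-week SD minimum is not met, or if the first CR, PR or SD comes after new therapy. A first scan on days 35 to 41 misses the minimum. That is 7 of 15 in-window days (46.7%) with ±7 days, and 7 of 8 (87.5%) in the Part C doxorubicin schedule. It matters only if no later scan qualifies.

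**The case against.** The strongest reply is that the study was not designed to assess efficacy, as SAP 5.3.2 and 5.8 both say. ORR is descriptive, the SAP refers to RECIST 1.1, and protocol Attachment 8 already holds the cut-off. The lack of a threshold does limit the severity. The general RECIST reference does not settle the matter, because the SAP then writes its own, different window.

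Several stronger readings are tempting, and the documents do not support them.

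- **Attachment 8 itself demands confirmation at 4 weeks.** Its best-response text only takes account of any such requirement. Its 4-week text is written for trials with response as the primary end point, which this one is not. The study-specific rule is the 6-week one in protocol 8.3.
- **The 4-week and 6-week texts contradict each other outright.** A scan at 6 weeks or later also satisfies a 4-week minimum. They are a stricter study rule beside general text. The difficulty is that a programmer could still defend 4 weeks, 6 weeks or no confirmation.
- **Nearly half of responses would be lost under 6 weeks.** The 46.7% is the share of next scans falling before day 42 under an assumed even spread. Only responses that are gone, or not imaged, by the following scan are lost.
- **Lack of confirmation inflates DCR.** It hardly moves DCR, as step 5 shows.
- **Responses to later therapy will be counted.** That depends on which of the conflicting follow-up texts sites apply.

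**Conclusion.** The point holds as a discrepancy between SAP and protocol, and within the SAP. Best overall response lacks the new-therapy cut-off that Attachment 8 sets and that the SAP's own time-to-event rules reflect, and it lacks the confirmation that protocol 8.3 calls for. The cut-off is the firmer half: adding it removes a possible upward bias in both ORR and DCR. Confirmation bears on ORR.

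The size is about 5 points of ORR per reclassified patient in an arm of 20. How many patients would be affected cannot be derived from the documents, and the response counts shown are illustrations. A reader might infer that the recommended dose is at risk. It is not, since the primary endpoint is DLT and PK exposure matching and no decision depends on ORR. Severity is minor to moderate.

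**What to change.** In SAP 5.3.2:

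- Define best overall response from first dose to the earlier of progression or start of new anticancer therapy.
- State that CR/PR counted in ORR is confirmed, at one interval, after reconciling protocol 8.3 (at least 6 weeks, study-specific) with Attachment 8 (at least 4 weeks, written for another setting). In making the choice, note that every adjacent on-schedule pair of scans meets 4 weeks, while some miss 6 weeks and would need the following scan. A 4-week rule can only hold or raise ORR relative to 8.3.
- Class unconfirmed CR/PR as SD where the 6-week SD minimum of Attachment 8 is met, and state that minimum for DCR.
- Apply the RANO or Macdonald rules to CNS tumors, since Attachment 8 covers RECIST only.

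In the protocol, reconcile section 8.3 and footnote b of the Attachment 1 follow-up schedule with that schedule's imaging comment on scans after new therapy.

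The cost is a few sentences. No new data are needed, because protocol 8.3 already records start dates of subsequent anticancer treatment for the patients concerned. The downside is that ORR may be slightly lower than under the SAP as written.

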7.2.2. Dosing Schedule

If any study drug is discontinued (olaratumab or chemotherapy), the patient will be discontinued from the trial. A change of body weight $\geq 10\%$ (increase or decrease) from baseline will result in re-calculation of dose to be administered.

The following treatments will be administered in this study every 3-week (21-day) ± 3 day cycle ([Table JGDN.7.1](#) and [Table JGDN.7.2](#)).

Part A:

Cycle 1

Olaratumab as IV infusion on Day 1 and Day 8 (at 15 mg/kg)

Cycle 2 and beyond

Olaratumab as IV infusion on Day 1 and Day 8 (at 15mg/kg, or 10 mg/kg if de-escalated),

AND

Doxorubicin as IV infusion on Day 1 and Day 2 (at 37.5 mg/m²; up to 6 cycles or a cumulative dose of 450 mg/m²)

OR

Vincristine as IV on Day 1 and Day 8 (patients ≥ 10 kg: 1.5 mg/m², patients <10 kg: 0.05 mg/kg. Dose is capped at 2 mg) plus irinotecan as IV on Days 1, 2, 3, 4, 5 (at 50 mg/m²),

OR

Ifosfamide as IV on Days 1, 2, 3, 4, and 5 (at 2.8 g/m²; up to 6 cycles or a cumulative dose of 84 g/m²). Treatment beyond 84 g/m² requires consultation with the Lilly CRP/CRS.

Part B:

Cycle 1

Olaratumab as IV infusion on Day 1 and Day 8 (at 20 mg/kg)

Cycle 2 and beyond

Olaratumab as IV infusion on Day 1 and Day 8 (at 20 mg/kg),

AND

Doxorubicin as IV infusion on Day 1 and Day 2 (at 37.5 mg/m²; up to 6 cycles or a cumulative dose of 450 mg/m²)

OR

Vincristine as IV on Day 1 and Day 8 (patients ≥ 10 kg: 1.5 mg/m², patients <10 kg: 0.05 mg/kg. Dose is capped at 2 mg) plus irinotecan as IV on Days 1, 2, 3, 4, 5 (at 50 mg/m²),

OR

Ifosfamide as IV on Days 1, 2, 3, 4, and 5 (at 2.8 g/m²; up to 6 cycles or a cumulative dose of 84 g/m²). Treatment beyond 84 g/m² requires consultation with the Lilly CRP/CRS.

Part C:

All Cycles

Olaratumab as IV infusion on Day 1 and Day 8 (at 20 mg/kg),

AND

Doxorubicin as IV infusion on Day 1 and Day 2 (at 37.5 mg/m²; up to 6 cycles or a cumulative dose of 450 mg/m²)

OR

Vincristine as IV on Day 1 and Day 8 (patients \geq 10 kg: 1.5 mg/m², patients <10 kg: 0.05 mg/kg. Dose is capped at 2 mg) plus irinotecan as IV on Days 1, 2, 3, 4, and 5 (at 50 mg/m²),

OR

Ifosfamide as IV on Days 1, 2, 3, 4, and 5 (at 2.8 g/m²; up to 6 cycles or a cumulative dose of 84 g/m²). Treatment beyond 84 g/m² requires consultation with the Lilly CRP/CRS.

Table JGDN.7.1. Treatment Regimens/Dosing Schedule (Parts A and B)

Study Drug		Dose	Route	Timing

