**Table JGDN.5.1. Censoring Rule of PFS Primary Analysis**

Situation	Event / Censor	Date of Event or Censor
Tumor progression or death	Event	Earliest date of PD or death
No tumor progression and no death	Censored	Date of last adequate radiological assessment or date of first study dose
unless		
No baseline radiological tumor assessment available	Censored	Date of first study dose
No adequate postbaseline radiological tumor assessment available and death reported after 2 scan intervals following first study dose	Censored	Date of first study dose
New anticancer treatment started and no tumor progression or death within 14 days	Censored	Date of adequate radiological assessment prior to (start of new therapy +14 days) or date of first study dose (whichever is later)
Tumor progression or death documented immediately after 2 or more consecutive missing scan intervals following last adequate radiological tumor assessment or first study dose (whichever is later)	Censored	Date of last adequate radiological assessment prior to the missing assessment or date of first study dose

Abbreviations: CR = complete response; PD = progressive disease; PFS = progression free survival; PR = partial response; SD = stable disease.

- a Symptomatic deteriorations (that is, symptomatic progressions, which are not radiologically confirmed) will not be considered as disease progressions.
- b Adequate radiological tumor assessment refers to an assessment with one of the following responses: CR, PR, SD, or PD.
- c The 2-scan interval is counted from the date of last adequate tumor assessment to the date of next 2 scheduled tumor assessments plus 14 days (adjusted by tumor assessment window).
- d Refer to flow chart in [Appendix 1](#) if a patient meets multiple censoring criteria.
- e If there are multiple dates associated with 1 assessment, the assessment date will be set to the first date when the overall response is PD and the last date otherwise.

**Overall survival (OS)** is defined as the time from the date of first study dose to death due to any cause. Patients will be censored at the date of last known alive.

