## 5.8. Efficacy Analyses

The study was not designed to make an efficacy assessment. Exploratory efficacy analysis will be performed to investigate antitumor activity within each combination arm. The efficacy analysis will include all treated patients (ie. Safety Population). Tumor response data will be tabulated according to dose cohort and combination arm. A listing of best overall response will be provided by cohort. Best overall response will be summarized by dose cohort and combination arm. The objective response rate (ORR=CR+PR) and disease control rate (DCR=CR+PR+SD) along with the 90% exact confidence interval (CI) will be tabulated for each cohort and combination arm. For patients having CR/PR, the median duration of response,

together with a 90% CI will be estimated using Kaplan-Meier method. The median PFS will be estimated along with 90% CI by dose cohort and combination arm, using Kaplan-Meier method.

Any deaths observed during the study will be summarized descriptively and possibly interpreted in the context of study drug dose for each patient observed to have died. Dependent on the maturity of the data, overall survival may be analyzed using time-to-event methods, such as Kaplan-Meier.

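### SAP 5.3.2 gives a responder who starts other antitumor therapy without progression two conflicting statuses in duration of response

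*SAP*

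**What the plan says.** - **SAP 5.3.2, first sentence.** Duration of response starts at the first CR or PR and runs until PD is documented, "or initiation of other/additional antitumor therapy is first reported, or death". The three ends stand in one list, and none is labelled as an event or as a censoring point.
- **SAP 5.3.2, next sentence.** "Patients who do not relapse are censored at the day of their last tumor assessment". It has no separate rule for new therapy.
- **SAP Table JGDN.5.1 (PFS only).** If new anticancer treatment starts and no progression or death follows within 14 days, the patient is censored at "Date of adequate radiological assessment prior to (start of new therapy +14 days) or date of first study dose (whichever is later").
- **SAP 5.8.** For patients with CR or PR, the median duration of response "together with a 90% CI will be estimated using Kaplan-Meier method".
- **Protocol Attachment 8.** Duration of overall response runs "until the first date that disease is recurrent or objective progression is observed". It lists neither new therapy nor death.
- **Protocol 7.2.2.** Doxorubicin is given for "up to 6 cycles or a cumulative dose of 450 mg/m²" and ifosfamide for "up to 6 cycles or a cumulative dose of 84 g/m²"; ifosfamide beyond that dose needs consultation with the sponsor. Vincristine/irinotecan has no cap.
- **Protocol Attachment 1.** The Parts A/B schedules for doxorubicin and ifosfamide stop olaratumab and take the patient off study at the chemotherapy maximum. The Part C schedules carry no such statement.

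**The concern.** A responder who moves to other therapy while still in response fits both sentences of SAP 5.3.2. Under the first, taken literally, the response ends on the date the new therapy is reported. Under the second, the patient is censored at the last scan. Status and date both differ, so two programmers could report different medians from the same data. Under the literal reading, one patient can be censored and progression-free for PFS and yet have lost the response.

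The design makes this case likely in two of the three arms. A fixed number of chemotherapy cycles, followed in Parts A/B by removal from study, brings patients off treatment whether or not they are still responding. If some then start other treatment, the literal reading shortens the Kaplan-Meier median for a reason set by the schedule and not by the tumor. Vincristine/irinotecan has no cap, so the distortion could differ between arms. Protocol 6.2 aims for about 20 evaluable patients per combination arm. Responders will be fewer, so reclassifying one or two can move a median.

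**Working it through.** **1. The caps.** Inputs are from Protocol 7.2.2.
- Doxorubicin: 6 cycles × 2 days × 37.5 mg/m² = 450 mg/m².
- Ifosfamide: 6 cycles × 5 days × 2.8 g/m² = 84 g/m².

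Both reproduce the stated figures exactly, so at full dose the cycle cap and the dose cap fall together.

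**2. When the cap is reached.** Cycles last 3 weeks. Parts A/B start chemotherapy in Cycle 2, so the sixth chemotherapy cycle is Cycle 7 and ends at week 7 × 3 = 21. In Part C it is Cycle 6 and ends at week 6 × 3 = 18.

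**3. Longest duration under the literal reading, if new therapy starts as soon as the cap is reached.** Scans are every 2 cycles, so the first two fall at weeks 6 and 12. Months = weeks × 7 / 30.4375 (SAP 5.3).

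| First response | Parts A/B | Part C |
|---|---|---|
| Week 6 | 21 − 6 = 15 weeks (3.4 months) | 18 − 6 = 12 weeks (2.8 months) |
| Week 12 | 21 − 12 = 9 weeks (2.1 months) | 18 − 12 = 6 weeks (1.4 months) |

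None of these patients has progressed. The Part C column also assumes that the patient leaves treatment at the cap, which the Part C schedules do not state.

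**4. Effect on the Kaplan-Meier median.** The documents give no response duration and no rate of new therapy, so this step is a simulation under assumptions (200,000 responders per scenario):
- true duration exponential, with median 4, 6 or 12 months;
- response first seen at week 6 or week 12 with equal probability;
- 25% to 100% of those still responding start new therapy 0 to 6 weeks after the cap;
- follow-up to week 104.

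The censored version uses the last 6-weekly scan on or before the start of new therapy. The 14-day allowance of Table JGDN.5.1 is not modelled. Cells show the median in months, new therapy as an event / censored.

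| Part | True median | 25% start | 50% start | 75% start | 100% start |
|---|---|---|---|---|---|
| A/B | 4 | 3.3 / 3.8 | 3.0 / 3.7 | 2.8 / 3.4 | 2.6 / 3.2 |
| A/B | 6 | 4.2 / 5.8 | 3.5 / 5.5 | 3.1 / 5.0 | 2.9 / 4.2 |
| A/B | 12 | 7.0 / 11.8 | 4.1 / 11.5 | 3.5 / 10.8 | 3.2 / 4.3 |
| C | 6 | 3.8 / 5.8 | 3.0 / 5.5 | 2.6 / 4.7 | 2.3 / 3.0 |

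The gap widens as the true duration lengthens. Censoring is not exact either. Patients who progress between the last scan and the new therapy still count as events, while those who stay in response are censored back at that scan. At 100%, both readings fall well below the truth.

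**The case against.** The strongest reply is that the SAP never calls new therapy an event. The first sentence may only say where measurement stops, with the second supplying the status. On that reading the patient is censored, much as for PFS, and no bias arises. This stands in part: a reader might infer that the SAP plainly adopts an event rule, and the text does not support that. What it contains is a contradiction, because new therapy stands beside PD and death and nothing says which sentence governs.

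The conflict with the protocol is also the weaker limb. Attachment 8 is general RECIST text, Protocol 10.7 does not mention duration of response, and it leaves details to the SAP. Ending observation at new therapy also agrees with Attachment 8's window for best overall response and with the follow-up schedule, which lets imaging stop there. These points justify stopping the clock, but not recording a loss of response.

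A reader might also infer that the cap itself ends the response in every arm. It does not. The cap acts only through new therapy started afterwards, and vincristine/irinotecan has none. The explicit stop at the cap is in the Parts A/B schedules only. Protocol 6.2 allows olaratumab alone after chemotherapy, while Protocol 7.2.2 takes a patient off the trial when any study drug is discontinued. These passages need to be reconciled.

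**Conclusion.** The point holds as a contradiction within SAP 5.3.2. One of its two readings also conflicts with the SAP's PFS rule and with Attachment 8. It should be settled before analysis.

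With a true median of 6 months and half of ongoing responders starting new therapy after the cap, the median is 3.5 months (Parts A/B) or 3.0 months (Part C) if new therapy is an event, against 5.5 months if it is censored. Over 25% to 75% starting new therapy in Parts A/B, the ranges are 3.1 to 4.2 against 5.0 to 5.8 months. These figures apply to the capped arms only and rest on assumptions that the documents neither give nor contradict.

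A reader might go further and expect a median of about 12 weeks against one that is not reached. That needs half of the responders to start new therapy at the Part C cap and almost no progression or death among the rest. With no other events, any share below half leaves the median unreached on both readings, so that contrast comes from the assumption.

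The consequence is limited. SAP 5.3.2 and 5.8 say that the study was not designed to assess efficacy, the analyses are descriptive, and the primary objective does not use duration of response.

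**What to change.** In SAP 5.3.2:

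1. Define the end-of-response event as PD or death from any cause, and delete the clause on other or additional antitumor therapy.
2. Replace the censoring sentence. Responders without PD or death are censored at the last adequate assessment. If new anticancer therapy starts first, apply the handling in Table JGDN.5.1, including its 14-day allowance, with the date of first response replacing the date of first dose as the floor. The present sentence would also censor a responder who dies without relapse, so it cannot stay as it is.
3. State that counting death extends the Attachment 8 definition.

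Separately, reconcile Protocol 6.2, Protocol 7.2.2 and the Attachment 1 schedules on what follows when the chemotherapy maximum is reached. This review takes no position on which should prevail.

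For the definition itself the cost is SAP wording only. Protocol 8.3 and the Attachment 1 follow-up schedule already collect subsequent therapy dates. One downside remains: the follow-up schedule lets scanning stop at new therapy, so the censoring may be informative. Reporting the number of responders censored for this reason, by arm, would let readers judge it.
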